### 10.4 Randomization:

Patients will be randomized into arms 1 and 2 using R (R Core Team. 2012) at time of registration (if screening labs are to be obtained on same day as treatment randomization may be performed at the time all other eligibility criteria are informally confirmed to allow adequate time for treatment planning). The UC Project Manager will work with the statistician to ensure each patient is assigned to one of the arms correctly. Randomization of patients does not affect the primary or secondary endpoints of this study as response and safety is based on the combination treatment in which both groups will receive. The patients are randomized for the exploratory endpoints in order to better understand the difference of effects of metformin versus pembrolizumab on the immune system.

## ADVERSE EVENTS: LIST AND REPORTING REQUIREMENTS

### 11.1 Adverse event definition, attributions, and expectedness

An Adverse Event (AE) is defined as any new untoward medical occurrence or worsening of a preexisting medical condition in a clinical investigation participant administered study drug and that does not necessarily have a causal relationship with this treatment. An AE can therefore be any unfavorable and unintended sign (such as an abnormal laboratory finding), symptom, or disease temporally associated with the use of investigational product, whether or not considered related to the investigational product.

The causal relationship to study drug is determined by a physician and should be used to assess all adverse events (AE). The causal relationship can be one of the following:

- Unrelated – The AE is clearly NOT related to the study intervention
- Unlikely – The AE is doubtfully related to the study intervention
- Possible – The AE may be related to the study intervention
- Probable – The AE is likely related to the study intervention
- Definite – The AE is clearly related to the study intervention

The expectedness of the occurrence of an adverse event is determined by a study physician and should be used to help determine whether prompt reporting requirements to regulatory authorities (IRB, FDA etc.) are required.

- Expected – An adverse event is expected if it is described as an anticipated risk described within this protocol or research informed consent form as a known adverse event/risk.
- Unexpected – If an adverse event is not described within this protocol or consent form as an expected risk to subjects then the AE will be considered to be unexpected.

Adverse events can be spontaneously reported or elicited during open-ended questioning, examination, or evaluation of a subject.

## 11.2 Serious adverse events definition

A Serious Adverse Event (SAE) is any untoward medical occurrence that at any dose:

- Results in death
- Is life-threatening (defined as an event in which the participant was at risk of death at the time of the event; it does not refer to an event which hypothetically might have caused death if it were more severe)
- Requires inpatient hospitalization or causes prolongation of existing hospitalization (See NOTE below).
- Results in persistent or significant disability/incapacity
- Is a congenital anomaly/birth defect
- Is an important medical event - defined as a medical event(s) that may not be immediately life-threatening or result in death or hospitalization but, based upon appropriate medical and scientific judgment, may jeopardize the subject or may require intervention (e.g., medical, surgical) to prevent one of the other serious outcomes listed in the definition above. Examples of such events include, but are not limited to, intensive treatment in an emergency room or at home for allergic bronchospasm; blood dyscrasias or convulsions that do not result in hospitalization.

Although pregnancy, overdose, and cancer are not always serious by regulatory definition, these events must be handled as SAEs.

NOTE: The following hospitalizations are not considered SAEs:

- A visit to the emergency room or other hospital department < 24 hours, that does not result in admission (unless considered an important medical or life-threatening event)
- Elective surgery, planned prior to signing consent
- Admissions as per protocol for a planned medical/surgical procedure
- Routine health assessment requiring admission for baseline/trending of health status (e.g., routine colonoscopy)
- Medical/surgical admission other than to remedy ill health and planned prior to entry into the study. Appropriate documentation is required in these cases
- Admission encountered for another life circumstance that carries no bearing on health status and requires no medical/surgical intervention (e.g., lack of housing, economic inadequacy, caregiver respite, family circumstances, administrative reason).

- Admission for administration of anticancer therapy in the absence of any other SAEs.

### **11.3 Serious Adverse Event Collection and Reporting**

All Serious Adverse Events (SAEs) that occur following the subject's written consent to participate in the study should be collected on institutional adverse event logs and reported using the applicable FDA MedWatch form within 24 hours of learning of the event to the University of Cincinnati PI and Project Manager and entered into REDCap. Sites should contact the UC Project Manager for copies of the MedWatch form.

SAEs must also be reported to the IRB of record, and/or FDA as needed based on applicable institutional and regulatory timeframes.

### **11.4 Adverse Event Collection and Reporting**

The collection of non-serious AE information should begin at initiation of study drug, all events prior to that time should be documented as medical history (BUT all SAEs must be collected from consent, see Section 11.3). All adverse events (not just those deemed to be treatment-related) should be collected continuously during the treatment period and for a minimum of 90 days following the last dose of study treatment.

Adverse events must be collected using institutional adverse event logs and captured in REDCap.

AEs should be followed to resolution or stabilization, or reported as SAEs if they become serious. Follow-up is also required for AEs that cause interruption or discontinuation of study drug and for those present at the end of study treatment as appropriate. Subjects with an AE of Grade > 1 that is at least possibly attributed to study treatment will be followed until the resolution of the AE to Grade 0-1 or until the beginning of a new anti-neoplastic therapy, whichever occurs first. SAEs that occur within 90 days of the end of treatment or before initiation of a new anti-cancer treatment should also be followed and recorded through resolution.

### **11.5 Other safety considerations**

Any significant worsening noted during interim or final physical examinations, electrocardiograms, X-rays, and any other potential safety assessments, whether or not these procedures are required by the protocol, should also be recorded as a non-serious or serious AE, as appropriate, and reported accordingly.

### **11.6 Evaluation of adverse events and grade changes**

An investigator who is a qualified physician will evaluate all adverse events according to the NCI Common Terminology for Adverse Events (CTCAE), version 5.0. Any adverse event which changes CTCAE grade over the course of a given episode will have each change of grade recorded within REDCap and within institution specific AE logs.

All adverse events regardless of CTCAE grade must also be evaluated for seriousness.

## 11.7 Pregnancy

Although not an adverse event in and of itself, pregnancy as well as its outcome must be documented in REDCap. Any pregnancy occurring in a patient or patient's partner from the time of consent to 4 months after the last dose of study drug must be reported and then followed for outcomes. Newborn infants should be followed until 30 days old.

## 11.8 Contraception/Birth Control

Participants of childbearing potential who are sexually active and their partners must agree to the use of a highly effective form of contraception throughout their participation. Effective birth control is considered to be:

- Combined (estrogen and progestogen containing) hormonal contraception associated with inhibition of ovulation:
- Oral route, Intravaginal route or Transdermal route
- Progestogen-only hormonal contraception associated with inhibition of ovulation
- Oral, Injectable, or Implantable
- Intrauterine device
- Intrauterine hormone-releasing system
- Bilateral tubal occlusion
- Vasectomized partner
- Sexual abstinence

## 11.9 Breast Feeding

Participants must not breast-feed while receiving protocol therapy and for 180 days following the last dose of protocol therapy.

## 11.10 Secondary Malignancy

A secondary malignancy is a cancer caused by treatment for a previous malignancy (e.g., treatment with investigational agent/intervention, radiation or chemotherapy). A secondary malignancy is not considered a metastasis of the initial neoplasm.

Any malignancy possibly related to cancer treatment (including AML/MDS) should also be reported via the routine reporting mechanisms outlined in Section 11 (AE reporting).

## 11.11 Second Malignancy

A second malignancy is one unrelated to the treatment of a prior malignancy (and is **NOT** a metastasis from the initial malignancy). Second malignancies require **ONLY** routine AE reporting unless otherwise specified.

## STUDY CALENDAR

Cycle	Screening	Lead in Treatment Before Cycle 1			1	2	3, 5, 7, 9 etc.	4, 6, 8, 10, etc.	Off Study / Safety follow-up (30 days post tx) i	Survival Follow-up
Day	28 days before 1st lead-in tx o	-21 c	-14	-7	1	1	1	1		
Window (days)				+/-1 day	+/-1 day	+/-3 days	+/-3 days	+/-3 days	+/-3 days	+/-4 weeks
Arm 1										
Metformin ER daily			X a	X b	X	X	X	X		
Pembrolizumab q 3 weeks or q 6 weeks a					X	X	X	X		
Correlative blood draws h			X h		X	X				
Arm 2										
Metformin ER daily				X a	X b	X	X	X		
Pembrolizumab q 3 weeks or q 6 weeks p		X			X	X	X	X		
Correlative blood draws h		X h		X		X				
Both Arms										
Informed consent	X									
Demographics	X									
Medical history	X									
Concomitant meds	X	X	X-----X							
Physical exam d	X	X	X	X	X		X		X	
Vital signs	X	X	X	X	X	X	X	X	X	
Height	X									
Weight	X	X	X	X	X	X	X	X	X	
Performance status	X k	X	X	X	X	X	X		X	
CBC w/diff, plts f	X k	X	X	X	X	X	X	X	X	
Serum chemistry f	X k	X	X	X	X	X	X	X	X	
Urinalysis	X k				X		X			
Coagulation tests	X k				X		X			
C-peptide	X k				X	X				
Thyroid Tests k	X k				X		X			
Vitamin B-12	X k				X	X				
Lactate (Lactic Acid)	X k				X	X				
Adverse event evaluation m		X-----X								
Pregnancy test e				X						
Radiologic evaluation l, q	X						X			
Correlative biopsy g	X					X				
Medication diary n	X		X	X	X	X	X	X		
Post-tx survival status j									X	X
a. Metformin ER starting dose 1000mg daily b. Metformin ER escalation dose 2000mg daily										

Cycle	Screening	Lead in Treatment Before Cycle 1			1	2	3, 5, 7, 9 etc.	4, 6, 8, 10, etc.	Off Study / Safety follow-up (30 days post tx) i	Survival Follow-up
Day	28 days before 1st lead-in tx o	-21 c	-14	-7	1	1	1	1		
Window (days)				+/-1 day	+/-1 day	+/-3 days	+/-3 days	+/-3 days	+/-3 days	+/-4 weeks

c. Only applies to Arm 2 as Arm 1 does not have a D -21.
 
d. Full physical exam at screening, directed on other visits
 
e. Child-bearing females only. Test within 72 hours of first treatment (See 7.6.1)
 
f. See table 1 in section 7.5.7
 
g. Archival acceptable at screening; Cycle 2 repeat biopsy if clinically feasible. Biopsy may be of a target or non-target lesion but if there is only one target lesion that is being followed, this lesion should be avoided for biopsy unless discussed with PI.
 
h. 60mls in EDTA tubes and 5mls in red top serum tube at Day -14 (Arm 1) or Day -21 (Arm 2); and also collect Day 1 (Arm 1) or Day -7 (Arm 2); and also collect Cycle 2 Day 1 (week 4). The Day -14 & Day -21 respective samples must be collected before any study treatment is given on those days – if this pre-treatment sample is missed then no other blood correlatives should be collected for those subjects. This first pre-treatment correlative blood sample may be obtained at another time-point after randomization but prior to first lead in treatment with the PI's approval.
 
i. Should be completed at 30 days post-treatment OR before new anti-cancer therapy whichever occurs first.
 
j. Every 3 months/12 weeks - can be completed by telephone
 
k. ECOG PS and screening laboratory tests to be completed within 10 days of first tx (may be performed on day 1 prior to tx)
 
l. Scans to be performed every 12 weeks +/- 5 days starting with C3D1
 
m. Adverse events should be collected for 90 days following the last dose of study treatment
 
n. Subjects will be provided with a medication diary at screening but will not complete entries until dispensed Metformin. The medication diary will be returned to research staff and a new diary issued at the end of each course.
 
o. Subjects are randomized to either Arm 1 or Arm 2 after registration (eligibility is confirmed). These arms are independent of each other. Each arm has the same amount of time 28 days, to complete screening activities before their respective first lead in treatment visits (Day -21 or Day -14).
 
p. Pembrolizumab may be given at 200mg q3 weeks or 400mg q6 weeks and may be changed during course of treatment per investigator discretion.
 
q. Temporarily discontinuing metformin in patients undergoing radiologic studies in which intravascular iodinated contrast media are utilized is left up to investigator discretion.
										

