#### NK Cell Infiltration and Tissue Biomarkers

- Collection of Specimen(s): Tumor block (if block is unavailable, 20 FFPE slides may be permissible but need verification from PI) will be collected at screening and Week 4; Archival is acceptable for pre-treatment
- Handling of Specimens(s): Normal operating procedures
- Shipping of Specimen(s): Ship per standard operating procedures; Notify CTO lab by email at [contact], ***the day of shipping the sample***.
- Site Performing Correlative Study: University of Cincinnati, [name] Laboratory

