## 7.4 Agent Administration

Treatment will be administered on an outpatient basis. Reported adverse events and potential risks are described in the Investigators Brochure for Pembrolizumab and the package insert for Metformin. Appropriate dose modifications are described in Section 8. No investigational or commercial agents or therapies other than those described below may be administered with the intent to treat the patient's malignancy.

Regimen Description					
Agent	Premedications; Precautions	Dose	Route	Schedule	Cycle Length
Pembrolizumab	No premedications; No steroids	200mg or 400mg	IV over 30 minutes	Days 1, week 1 (for 400mg	21 days (3 weeks)

				dose, therapy only given q6 weeks and on odd cycles)	
Metformin*	No premedications	1000mg for first 7 days followed by 2000mg daily	Oral	Daily	Continuous**

* The patient will be requested to maintain a medication diary of each dose of medication. The medication diary will be returned to research staff at the end of each course.
 
** Metformin will be escalated per schema and then given continuously throughout pembrolizumab cycles.
					

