Target lesions. All measurable lesions up to a maximum of 2 lesions per organ and 5 lesions in total, representative of all involved organs, should be identified as **target lesions** and recorded and measured at baseline. Target lesions should be selected on the basis of their size (lesions with the longest diameter), be representative of all involved organs, but in addition should be those that lend themselves to reproducible repeated measurements. It may be the case that, on occasion, the largest lesion does not lend itself to reproducible measurement in which circumstance the next largest lesion which can be measured reproducibly should be selected. A sum of the diameters (longest for non-nodal lesions, short axis for nodal lesions) for all target lesions will be calculated and reported as the baseline sum diameters. If lymph nodes are to be included in the sum, then only the short axis is added into the sum. The baseline sum diameters will be used as reference to further characterize any objective tumor regression in the measurable dimension of the disease.

Non-target lesions. All other lesions (or sites of disease) including any measurable lesions over and above the 5 target lesions should be identified as **non-target lesions** and should also be recorded at baseline. Measurements of these lesions are not required, but the presence, absence, or in rare cases unequivocal progression of each should be noted throughout follow-up.

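### The optional Cycle 2 biopsy may be taken from a RECIST target lesion, and section 13.1 has no rule for how that lesion then counts in the primary response

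*Combined protocol and SAP*

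**What the plan says.** **Choice of lesion.** Section 12, footnote g, makes the on-treatment sample conditional ("Cycle 2 repeat biopsy if clinically feasible") and then sets the choice of site: "Biopsy may be of a target or non-target lesion but if there is only one target lesion that is being followed, this lesion should be" left alone. That one restriction, for a patient with a single target, can be lifted by discussion with the PI. Nothing limits the choice in a patient with two to five targets.

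**Which lesions are targets.** Section 13.1.2 designates "All measurable lesions up to a maximum of 2 lesions per organ and 5 lesions in total". A measurable lesion therefore falls outside the sum only when a cap is already filled or it cannot be measured reproducibly. Section 13.1 does not ask which lesion was biopsied or by what technique, and does not say how to measure or code a target afterwards.

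**Tissue requested.** Section 6.2 asks for a tumor block at screening and week 4. Failing a block, "20 FFPE slides may be permissible but need verification from PI". The specimen schedule in 6.1 adds a tissue scroll. All tissue assays in 6.1 are marked O, which I read as optional, and 6.2 refers to a lab manual for details.

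**What depends on the sum.** Section 10.1 makes overall response by RECIST 1.1 and iRECIST the primary endpoint. Section 10.2 calls the study successful at 6 responders of 19. Section 10.4 explains that both arms receive the combination, so response is judged on all patients together.

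**Scan timing.** Footnote l starts scans at C3D1 and repeats them every 12 weeks. Section 7.6.3 says every 12 weeks without a start. Sections 13 and 13.1 say every 9 weeks.

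**The concern.** RECIST reads any change in the sum of diameters as a change in the tumor. If part of a target is cut out, the loss counts towards a PR; if it swells or bleeds after sampling, the gain counts towards PD. A procedure done for exploratory assays can thus alter the primary endpoint. There is no control arm in which the same error would cancel, and the go rule is a count in 19 patients.

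The protocol accepts the principle elsewhere. Section 4.2, criterion 2, allows palliative radiotherapy on study only when no target is irradiated, and footnote g itself shields a sole target. The shield stops at patients with two or three targets, where one lesion can still carry much of the sum.

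**Working it through.** **Inputs.** PR: a fall of at least 30% in the sum from baseline. PD: a rise of at least 20% and at least 5 mm from the smallest sum (both 13.1.4.1). Cycle length 21 days (7.4). Success at 6 of 19, assumed ORR 32% (10.2). Lesion sizes below are my assumptions; the documents give none.

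**1. Timing, reproducing the plan's own figure.** C2D1 = day 1 + 21 = 22, the first day of week 4, as footnote h states. C3D1 = day 1 + 42 = 43. The gap from biopsy to the footnote l scan is 43 − 22 = 21 days. It is 15 to 27 days with ±3 days on both visits, and 13 to 29 with ±3 on the biopsy visit and ±5 on the scan.

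Under the other statements the gap depends on where counting starts:

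| Count from | 9 weeks (63 days) | 12 weeks (84 days) |
|---|---|---|
| C1D1 | 63 − 21 = 42 | 84 − 21 = 63 |
| First lead-in dose, Arm 1 (about 14 days earlier) | 28 | 49 |
| First lead-in dose, Arm 2 (about 21 days earlier) | 21 | 42 |

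**2. Loss needed for a PR by biopsy alone.** For k equal targets of diameter d the sum is kd. A PR needs a fall of 0.30kd, which is a share 0.30k of one lesion.

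| Targets | Share one lesion must lose | Fall in sum if it is removed entirely |
|---|---|---|
| 2 | 60% | 50% |
| 3 | 90% | 33.3% |
| 4 | 120% (impossible) | 25% |
| 5 | 150% (impossible) | 20% |

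**3. Unequal and borderline cases.**
- Targets of 12 and 28 mm: removing the smaller gives 12/40 = 30%, exactly a PR.
- Targets of 15 and 25 mm: 15/40 = 37.5%.
- A 40 mm sum with a true fall of 18% (7.2 mm), plus 5 mm lost to biopsy: 12.2/40 = 30.5%, a PR.

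**4. Swelling.** Two 20 mm targets, otherwise unchanged: 20% of 40 mm is 8 mm, which also exceeds 5 mm, so 8 mm of swelling meets PD.

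**5. Effect on the decision.** One patient is 1/19 = 5.3 percentage points. At a true ORR of 32%, binomial with n = 19, exactly 5 responders has probability 0.18 and exactly 6 has 0.19. These are the chances of standing one patient either side of the rule, not the chance that a biopsy reclassifies anyone.

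**The case against.** The strongest reply is that the protocol has considered the matter and that the alarming examples are chosen. The biopsy is optional, depends on feasibility, may use a non-target lesion, and needs PI discussion before a sole target is touched. The cases in step 3 assume two targets and either complete removal of one or a patient already near the threshold. That criticism stands and limits the size of the point.

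A reader might infer three stronger things. The documents support none of them.
- **That the biopsied lesion will usually be a target.** No lesion counts or sites are given. Lesions beyond the caps are non-target, and nodes of 10 to under 15 mm are non-measurable.
- **That the tissue request implies excision.** Slides are thin sections: if each is 4 to 10 micrometers (my assumption), 20 use 0.08 to 0.2 mm of block depth. No passage calls for excision, and the lab manual is not available here.
- **That any procedural change passes straight into the result.** A PR or CR needs a confirmation scan at 4 weeks (7.6.3, 13.1). For swelling, 13.1 brings in iRECIST when pseudoprogression is suspected, and the notes in 13.1.4 allow a patient to stay on study at first progression.

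These safeguards are partial. Confirmation screens out transient shrinkage, but a lesion that has been removed is still absent 4 weeks later. Under RECIST 1.1 the PD would still be recorded, and 13.1.4.3 ends the best-response window at progression.

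**Conclusion.** The gap is real and modest. Footnote g permits biopsy of a target whenever two or more are followed, and of a sole target after PI discussion; section 13.1 has no rule for what follows. A small core would rarely cross a threshold by itself. The exposure is mainly excision of a small lesion, or a borderline sum, in patients with two or three targets. How many patients that is cannot be derived from the documents, so no expected bias in ORR can be given; only the value of one patient, 5.3 points, is firm.

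The 21-day gap rests on footnote l. Most readings of the 9- and 12-week statements give a longer one, which weakens the swelling argument but not the removal argument. Those scan statements must be reconciled in any case. The sample size is unaffected.

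An outright ban on biopsying a sole target might seem to follow. It goes further than needed, because footnote g deliberately leaves that case to discussion with the PI, and a sensitivity analysis can deal with it.

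**What to change.** 1. Amend footnote g and 13.1.2: where another measurable lesion exists, the lesion intended for the Cycle 2 biopsy is chosen at baseline and recorded as non-target. State this as an explicit exception to the rule in 13.1.2, which would otherwise forbid it.
2. Record the lesion and the technique for every on-treatment biopsy.
3. If a target is biopsied anyway, flag it and report a pre-specified sensitivity ORR with that lesion taken out of both the baseline and follow-up sums. In the 12 and 28 mm example, an unchanged second lesion then gives 28/28, no response, instead of 28/40, a PR.
4. If the biopsied lesion was the sole target, report ORR with and without that patient as a responder.
5. Reconcile footnote l, 7.6.3 and 13.1 on scan timing.

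**Cost.** Wording in one footnote and one definition, and two recorded items per biopsy; no added procedures. Some patients will have fewer lesions in the sum, and a patient with two measurable lesions will be judged on one. A lesion moved to non-target still counts for CR and for unequivocal progression, so the protection is not complete. Some optional exploratory samples may be lost. For patients already enrolled, steps 3 and 4 remain possible if the source records show which lesion was sampled.

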  13. Female subjects of childbearing potential should have a negative urine or serum pregnancy within 72 hours prior to receiving the first dose of study medication. If the urine test is positive or cannot be confirmed as negative, a serum pregnancy test will be required.
  14. Female subjects of childbearing potential should be willing to use 2 methods of birth control or be surgically sterile, or abstain from heterosexual activity for the course of the study through 4 months after the last dose of study medication. Subjects of childbearing potential are those who have not been surgically sterilized, or have not been free from menses for > 1 year.
  15. Male subjects should agree to use an adequate method of contraception starting with the first dose of study therapy through 4 months after the last dose of study therapy.

16. Must have adequate archival baseline tissue available (see tissue requirements) or new biopsy must be performed (section 6.2).

17. Ability to understand and the willingness to sign a written informed consent document.

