#### 7.4.1 Metformin

##### *Treatment:*

Patients will receive metformin ER starting on day -14 for arm 1 and Day -7 for arm 2. The starting dose will be 1000mg PO daily to be administered with evening meal. The tablet should be swallowed whole, and patients will be instructed not to crush, cut or chew medication. On day -7 (or Day 1 for arm 2), patients will increase to 2000mg daily. Metformin will be continued daily with pembrolizumab.

Metformin should continue throughout treatment and even through pembrolizumab delays unless patient is experiencing adverse effects attributed to metformin. Metformin should be taken with food at approximately the same time daily. Patients will be instructed to check their blood sugar if they have any symptoms of hypoglycemia including but not limited to chills/shakiness, cold feeling, lightheadedness, dizziness, etc. Patients will be given a diary to record each dose. They should also be warned that the shell of the ER tablet may be visible in stool and not to be alarmed.

NOTE: Temporarily discontinue metformin in patients undergoing radiologic studies in which intravascular iodinated contrast media are utilized. It is generally recommended that metformin be temporarily discontinued prior to or at the time of intravascular administration of iodinated contrast media (potential for acute alteration in renal function). Continue to withhold metformin for 48 hours after the radiologic study.

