### 7.6 Visit Requirements

Visit requirements are outlined in Section 12.0 - Study Calendar.

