### 7.6.1 Screening

Potential subjects will be evaluated to determine that they fulfill the entry requirements as set forth in eligibility requirements. Visit requirements are outlined in the Study Calendar.

Results of a test performed prior to the subject signing consent as part of routine clinical management are acceptable in lieu of a screening test if performed within the specified time frame. Screening procedures are to be completed within 28 days prior to the first dose of trial treatment except for the following:

- Laboratory tests and ECOG PS are to be performed within 10 days prior to the first dose of trial treatment.
- For women of reproductive potential, a serum pregnancy test will be performed within 72 hours prior to the first dose of trial treatment. A urine test may be considered if serum test is not appropriate.

Subjects may be rescreened after initially failing to meet the inclusion/exclusion criteria and they have not yet started treatment, however, re-screening tests will not be covered by study. Results from assessments performed during the initial screening period are acceptable in lieu of a repeat screening test if performed within the specified time frame and the inclusion/exclusion criteria is met.

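### The Study Calendar's only pregnancy-test mark is at Day -7, after first dosing in both arms, which contradicts inclusion 13, section 7.6.1 and the row's own footnote e

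*Combined protocol and SAP*

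**What the plan says.** **Eligibility and screening text.** Inclusion 13 (section 4.1) says that women of child-bearing potential "should have a negative urine or serum pregnancy within 72 hours prior to receiving the first dose of study medication". Section 7.6.1 sets the same 72-hour limit, also before the first dose. For the other screening tests it says: "Laboratory tests and ECOG PS are to be performed within 10 days prior to the first dose of trial treatment".

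**First dosing.** Treatment begins with a lead-in whose start differs by arm. Section 7.4.1 states: "Patients will receive metformin ER starting on day -14 for arm 1 and Day -7 for arm 2". In Arm 2 pembrolizumab comes first, on Day -21, according to the Arm 2 pembrolizumab row of the Study Calendar. Footnote o confirms the two starting days. It gives each arm 28 days to "complete screening activities before their respective first lead in treatment visits (Day -21 or Day -14".

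**Study Calendar (section 12).** The row labelled "Pregnancy test e" has one mark, in the Day -7 column, and its Screening cell is empty. Its footnote e reads "Child-bearing females only. Test within 72 hours of first treatment (See 7.6.1". Footnote k, attached to the Screening marks for performance status and laboratory tests, reads "ECOG PS and screening laboratory tests to be completed within 10 days of first tx (may be performed on day 1 prior to tx".

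**Standing of the calendar.** Section 7.6 says: "Visit requirements are outlined in Section 12.0 - Study Calendar". Sections 7.6.1 and 7.6.2 do likewise, and section 5.1 asks sites to send the baseline tests that the calendar requires when they register a patient.

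**The concern.** The grid and the text give different days for the same eligibility test. Pregnancy is an exclusion (section 4.2, item 13), so the test has to be known before any study drug is given. A test on Day -7 cannot serve that purpose: by then an Arm 1 patient has had a week of metformin, and an Arm 2 patient has had pembrolizumab two weeks before.

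The calendar is the working document for visits. A coordinator who builds the visit schedule from the grid could book the test for Day -7. The consequence would be exposure of a possibly pregnant patient and an eligibility deviation for each woman affected.

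Footnote k raises a lesser question of the same kind. It mentions Day 1, but neither arm is first dosed on a day that the calendar labels Day 1.

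**Working it through.** No sample size, power or error rate is involved. The check is to locate the mark, count days, and compare the provisions.

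**1. Position of the mark.** The calendar columns run Screening, Day -21, Day -14, Day -7, Cycle 1 Day 1, and so on. Counted by column separators, the pregnancy mark falls in the fourth column, Day -7. Two rows with known answers test this count. The Arm 2 metformin row has its first mark at the same offset, and section 7.4.1 puts that start on Day -7. The Arm 1 metformin row has its first mark one column earlier, at Day -14, again as in 7.4.1.

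**2. Days from first dose to the marked test** (test day minus first-dose day):

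| Arm | First dose | Marked test | Gap | With the column's ±1 day window |
|---|---|---|---|---|
| 1 | Day -14, metformin ER | Day -7 | -7 - (-14) = 7 days after | 6 to 8 days after |
| 2 | Day -21, pembrolizumab | Day -7 | -7 - (-21) = 14 days after | 13 to 15 days after |

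The limit is 72 hours, or 3 days. The gap exceeds it in both arms even at the early edge of the window, and the test falls on the wrong side of dosing.

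**3. The provisions side by side.**

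| Source | Timing of pregnancy test |
|---|---|
| Inclusion 13 | 72 hours or less before first dose |
| Section 7.6.1 | 72 hours or less before first dose |
| Footnote e | within 72 hours of first treatment, direction not stated, with a reference to 7.6.1 |
| Calendar row | Day -7 only |

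The first three agree once footnote e's reference to 7.6.1 is followed. The row agrees with none of them.

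**4. Number who could be affected.** The planned enrolment table has 1 + 7 + 1 = 9 women among 25 patients. The number of child-bearing potential is not given, so the plan supports only a range of 0 to 9.

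**5. Footnote k under its two readings.**
- Day 1 as the day of first treatment (Day -14 or Day -21): the gap is 0 days, before dosing. This agrees with the footnote's own 10-day limit and with sections 7.6.1 and 10.4 and footnote o.
- Day 1 as Cycle 1 Day 1: 14 days after first dose in Arm 1 and 21 in Arm 2 (15 and 22 if a Day 0 is counted). Both exceed the footnote's own 10 days and fall after treatment has begun.

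Only the first reading is coherent. The wording still invites the second, because every Day 1 column in the calendar is a cycle day, and footnote h uses Day 1 as distinct from Day -14 and Day -21.

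**The case against.** The best defence is that the governing text is already right. Footnote e ties the row to first treatment and cites 7.6.1, which says before the first dose. Inclusion 13 says the same, and section 5.1 requires every criterion to be verified at registration. A site would have to overlook all of these to test at Day -7. This stands as a limit on the claim: the grid could lead to late testing but does not prescribe it, and the fault is a clerical inconsistency in one row. It does not remove the conflict. The registration check is also not complete protection, since a Day -7 test cannot be among the baseline results sent in before lead-in dosing.

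A second objection is that the table was read from PDF and a merged lead-in cell could have shifted the mark. The two metformin rows argue against this, but the formatted table should be checked.

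A reader might go further and infer from footnote k that eligibility labs and ECOG may be taken after two or three weeks of study drug, leaving thyroid, lactate, coagulation, C-peptide, B-12 and urinalysis with only a post-treatment baseline. The documents do not support this. Footnote k sits on the Screening column, which is headed as the 28 days before the first lead-in treatment, and it requires the tests before treatment. Section 7.6.1 and footnote o put screening before the first lead-in dose, section 5.1 requires eligibility to be confirmed before an arm is assigned, and section 10.4 explains the allowance for labs drawn on the day of treatment. Those six tests have separate marks at Screening and at Cycle 1 Day 1, so two draws are planned, and none of them is an organ-function threshold in section 4.1. CBC, chemistry and performance status are marked on the lead-in days as well.

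**Conclusion.** The concern holds for the pregnancy test. The only calendar mark falls 7 days after first dose in Arm 1 and 14 days after in Arm 2, and it contradicts inclusion 13, section 7.6.1 and footnote e. This assumes that the extracted table keeps the true column. If the formatted table shows the mark before the lead-in dose, what remains is that footnote e does not itself say the test comes before treatment.

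The matter is safety-relevant and worth correcting, because sites schedule from this table. It has no bearing on the response endpoint, the sample size or any error rate. For footnote k the conclusion is limited to loose wording: Day 1 should be clarified, but the plan does not allow eligibility labs or ECOG after study drug.

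**What to change.** 1. Check the pregnancy-test row in the formatted protocol table.
2. Reconcile the row with inclusion 13 and section 7.6.1, so that the mark falls before the first lead-in dose of each arm (Day -14 in Arm 1, Day -21 in Arm 2). The row sits in the block for both arms, so a single mark in the Screening column governed by footnote e may be clearer than marks in two lead-in columns.
3. Have footnote e say that the test comes before the first dose of either study drug, and name the two days.
4. In the same edit, replace Day 1 in footnote k with the arm-specific first lead-in day.
5. For women already enrolled, compare test dates with first-dose dates in the site records.

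The change is one calendar row and two footnotes. It adds no test and sets no new rule, because it carries the protocol's existing eligibility timing into the calendar. The record check in step 5 covers at most the women enrolled so far.
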